3.7 PHARMACOKINETIC AND IMMUNOGENICITY ANALYSES

3.7.1 Pharmacokinetic Analyses

See the dedicated PK SAP.

3.7.2 Immunogenicity Analyses

Based on the immunogenicity analysis set, the immunogenicity assessment data will be presented according to the following categories.

- Number and percentage of subjects with positive ADA assays at baseline
- Number and percentage of subjects with at least one positive ADA assay at any time point following administration of the first dose
- Number and percentage of subjects with a positive treatment-induced ADA test at any time point after the first dose
- Number and percentage of subjects with a positive treatment-enhanced ADA test result at any time point after the first dose
- Number and percentage of subjects with a treatment-independent ADA test result at any time point after the first dose

- Number and percentage of subjects with an unevaluable ADA test result at any time point after first dose
- Overall ADA prevalence: total number and percentage of subjects with a positive treatment-induced ADA test result, a positive treatment-enhanced ADA test result, a treatment-independent ADA test result and an unevaluable ADA test result
- Overall ADA incidence: total number and percentage of subjects with a positive treatment-induced ADA test result and a positive treatment-enhanced ADA test result

Note: Treatment-induced ADA: The patient is ADA negative at baseline and ADA positive at any time after the first dose;

Treatment-enhanced ADA: The patient is ADA positive at baseline and has an enhanced ADA detection signal at any time point after the first dose (the immunogenicity titer is 4 times the baseline immunogenicity titer);

Treatment-independent ADA: The patient is ADA positive at baseline, and there is no enhancement in the ADA detection signal from the baseline titer at any time point after the first dose (the immunogenicity titer does not exceed the baseline immunogenicity titer), or the patient is ADA positive at baseline, and has all negative or deficient ADA test results after the first dose.

Unevaluable ADA: The patient is ADA deficient at baseline and ADA positive at least once at any time point after the first dose.

Those confirmed to be anti-CS1001 antibody positive were presented in the following categories.

- Number and percentage of subjects with a positive ADA neutralizing antibody (Nab) test result at baseline.
- Number and percentage of subjects with at least one positive Nab test result at any time point after the first dose.

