Planned number of subjects:	Phase Ib: Approximately 12 subjects will be enrolled Phase II: Approximately 40 subjects will be enrolled
Dose limiting toxicity (DLT) definition:	
Definition of DLT: All toxicity or adverse events (AEs) are graded according to NCI-CTCAE 5.0. Any AE occurring during C1 (21 days) that is not clearly caused by something other than investigational drug:
 
Hematological toxicity:
 
 • Grade 4 neutropenia that lasts for >7 days; • Grade ≥3 febrile neutropenia (ANC<1,000/mm³, with a single temperature of ≥38.3°C or a sustained temperature of ≥38°C for more than one hour); • Grade 3 neutropenia with infection;

	
 ● Grade 3 thrombocytopenia with clinically significantly bleeding; ● Grade 4 thrombocytopenia; ● Grade ≥ 4 anemia
	
Non-hematological toxicity:
 
 ● Grade ≥ 4 toxicity; ● Grade 3 toxicity that fails to be resolved to \leqGrade 2, with the exception of diarrhea, nausea and vomiting; ● Grade ≥ 3 immune-related adverse event (irAE); ● Any Grade 3 tumor flare reaction (local pain, irritation or rash at known or suspected tumor focus) that lasts for 7 days or above; ● Grade 3 or Grade 4 non-hematological laboratory abnormalities, if meet any of the followings: 
 – need medical intervention – require hospitalization – last for >7 days 
and other toxicity of any grade that requires premature termination of the study as determined by the investigator and the sponsor through discussion.
 
Definition of MTD: Based on BOIN design, MTD is the highest dose level at which 30% of the subjects experience DLT within 21 days (Cycle 1) among which at least 6 subjects are available for DLT evaluation. The RP2D will be determined by SMC based on comprehensive data of safety and tolerability, PK, pharmacodynamics, and preliminary anti-tumor efficacy obtained during the dose escalation phase. The RP2D will not exceed the MTD and will be determined at a dose escalation meeting.

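### SAP 3.7.2 has no ADA class for a baseline-positive subject whose peak titer rises above baseline but stays below four times it, so overall ADA prevalence omits that subject

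*SAP*

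**What the plan says.** SAP section 3.7.2 first gives two plain tallies: subjects positive at baseline, and subjects with any positive result after the first dose. These are the two tallies that protocol section 10.6 lists. The SAP then adds four classes and two totals that the protocol does not define.

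- **Treatment-induced:** "The patient is ADA negative at baseline and ADA positive at any time after the first dose".
- **Treatment-enhanced:** baseline-positive with a stronger signal after dosing, explained in parentheses as "the immunogenicity titer is 4 times the baseline immunogenicity titer".
- **Treatment-independent:** baseline-positive with no strengthening of the signal, explained in parentheses as "the immunogenicity titer does not exceed the baseline immunogenicity titer"; or baseline-positive and the subject "has all negative or deficient ADA test results after the first dose".
- **Unevaluable:** "The patient is ADA deficient at baseline and ADA positive at least once at any time point after the first dose".

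The first total begins "Overall ADA prevalence: total number and percentage of subjects with a positive treatment-induced ADA test result" and goes on to add the enhanced, independent and unevaluable classes. The second is "Overall ADA incidence: total number and percentage of subjects with a positive treatment-induced ADA test result and a positive treatment-enhanced ADA test result".

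**The concern.** The four classes should cover every subject with a positive ADA result, because prevalence is built by adding them up. They do not. The two definitions open to a baseline-positive subject use different cut-points, one at four times baseline and the other at baseline itself, and nothing covers the interval between.

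A programmer who follows the text would leave such a subject unclassified and out of prevalence. The results table would then fail to reconcile, because enhanced plus independent would be smaller than the baseline-positive count printed a few rows above. The ordering would also be odd. A baseline-positive subject with no positive result after dosing counts towards prevalence, while one whose titer doubled does not. The alternative is that the programmer closes the gap by an unrecorded judgement, which another programmer might make differently.

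**Working it through.** The plan states no figure to reproduce, so the check is logical. The arithmetic is used only to size the effect.

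**Step 1: which classes are open to a baseline-positive subject.** Treatment-induced needs a negative baseline, and unevaluable needs a missing one. Only enhanced and independent remain.

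**Step 2: classify by titer ratio.** Let R be the highest post-dose titer divided by the baseline titer, with R = 0 when all post-dose results are negative or missing.

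| R | SAP, threshold read as at least 4x | SAP, threshold read as exactly 4x | Amended definitions |
|---|---|---|---|
| 0, 0.5, 1 | independent | independent | independent |
| 1.5, 2, 3, 3.99 | none | none | independent |
| 4 | enhanced | enhanced | enhanced |
| 8, 16 | enhanced | none | enhanced |

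The interval 1 < R < 4 has no class under either reading of the threshold.

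**Step 3: effect on the totals.**

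- Prevalence = (induced + enhanced + independent + unevaluable) / N. A subject with 1 < R < 4 adds nothing to the numerator, so k such subjects lower prevalence by k/N.
- Incidence = (induced + enhanced) / N. Such a subject is not enhanced, so incidence does not change when the threshold is read as at least 4x.
- The baseline-positive and any-post-dose-positive tallies both include the subject.

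**Step 4: size per subject.** SAP section 3.1 summarises Phase Ib by dose group and Phase II in aggregate, so those groups supply the denominators. The SAP synopsis plans as follows: "Phase Ib: Approximately 12 subjects will be enrolled Phase II: Approximately 40 subjects will be enrolled". Assuming every subject has ADA data, as the immunogenicity analysis set requires:

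- Phase II, N = 40: 1/40 = 2.5 percentage points.
- Phase II with the optional 15 extra FGF19 IHC+ subjects, N = 55: 1/55 = 1.8 points.
- All of Phase Ib, N = 12: 1/12 = 8.3 points.
- A Phase Ib dose group of 6, as an illustration: 1/6 = 16.7 points.

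**Step 5: does the amendment close the gap?** With enhanced as R ≥ 4 and independent as every other baseline-positive subject, each R in the table falls in exactly one class. Enhanced plus independent then equals the baseline-positive count. Prevalence becomes every subject with at least one positive result, at baseline or later: all baseline-positive subjects, plus the induced (baseline negative, later positive), plus the unevaluable (baseline missing, later positive).

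**The case against.** The best case for leaving the text alone has five parts.

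- **Intended meaning.** The lead words of the independent class mirror those of the enhanced class, and enhancement is defined by the four-fold threshold. No enhancement might therefore simply mean less than four-fold. That is probably what was meant, but the parenthesis attached to it restricts the class to titers no higher than baseline. Closing the gap this way means overriding the written rule.
- **Link to the endpoint.** A reader might infer that the secondary endpoint, occurrence of anti-CS1001 antibody, is undercounted. The documents do not support that. The two tallies listed in protocol section 10.6 are both in the SAP, and the affected subject is in both. The error is confined to a derived SAP total.
- **Incidence.** A reader might also infer that incidence is undercounted, because the wording lacks an at-least and an 8-fold rise is not exactly 4-fold. This needs a reading that excludes the strongest responses from a class meant to capture enhancement. It is a wording fault worth correcting, not evidence of a biased incidence.
- **Number of subjects.** A reader might assume a baseline-positive rate and multiply. At 5%, 0.05 × 52 = 2.6 subjects; across 2% to 10% and totals of 52 to 67 (12 + 40 to 12 + 55), the result runs from about 1 to about 7. The documents give no such rate for patients. The product also counts every baseline-positive subject, whereas only those with a rise between 1x and 4x are lost. It is a ceiling under an assumption, and the pooled denominator matches no summary in the plan.
- **Dilution series.** Neither document states the titer steps. If they are two-fold, only a ratio of 2 falls in the gap; if four-fold, nothing does. This stands as a reason why the gap may stay empty, but it does not make the definitions complete.

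**Conclusion.** The gap is real on the SAP's own wording, and nothing else in the SAP or protocol closes it. A baseline-positive subject with a highest post-dose titer above 1x but below 4x baseline belongs to no class and is left out of overall ADA prevalence. Each such subject costs 1/N of the reported group, with the sizes given in the working. Those sizes assume planned enrolment and ADA data for everyone. The number of subjects affected is unknown and may be zero.

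The consequence is limited to a descriptive total and its reconciliation with the baseline-positive row. No go or no-go criterion uses ADA. The point is still worth correcting, because the rule as written can give a wrong figure and the correction is very small.

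**What to change.** Amend two definitions in SAP section 3.7.2:

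- Treatment-enhanced: ADA-positive at baseline, with any post-dose titer at least 4 times the baseline titer.
- Treatment-independent: every other subject who is ADA-positive at baseline, including those whose post-dose results are all negative or missing.

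Add a programming check that the two classes sum to the baseline-positive count in each reported group. The prevalence and incidence formulas can stay as they are. The cost is two sentences of text, best settled before database lock and before the ADA tables are programmed. No extra data are needed.

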3.8 BIOMARKER ANALYSES

Measurement of biomarkers, such as the expression of FGF19 and PD-L1 in tumor cells and tumor-infiltrating immune cells prior to treatment, will be presented based on available data. The correlation between measurement of the above indicators and clinical outcomes (e.g., antineoplastic efficacy) will be described in graphical and tabular forms.

3.9 MISSING VALUES

Processing of missing values: Missing values will not be imputed. The processing and censoring of missing data for the efficacy portion is described in Section 3.5. For missing dates, please refer to Appendix 3 for the specific imputation method for calculation. The dates in the list will be listed as filled on the eCRF.

3.10 INTERIM ANALYSIS

No interim analysis is planned for this study.

4. LIST OF ABBREVIATIONS

Abbreviation	Full name of abbreviations	Chinese Name
ADA	Anti-drug Antibody	抗药抗体
AE	Adverse Event	不良事件
ALP	Alkaline Phosphatase	碱性磷酸酶
ALT	Alanine Transaminase	丙氨酸氨基转移酶
AST	Aspartate Transaminase	天冬氨酸氨基转移酶
ATC	Anatomical Therapeutic Chemical	解剖学治疗学及化学分类系统
CI	Confidence Interval	置信区间
CR	Complete Response	完全缓解
CT	Computed Tomography	计算机断层
CTCAE	Common Terminology Criteria for Adverse Events	不良反应通用术语事件标准
CV	Coefficient of Variation	变异系数
DCR	Disease Control Rate	疾病控制率
DLT	Dose-Limiting Toxicity	剂量限制性毒性
DOR	Duration of Response	缓解持续时间
EAS	Efficacy Analysis Set	有效性分析集
ECOG	Eastern Cooperative Oncology Group	美国东部肿瘤协作组
ECG	Electrocardiography	12 导联心电图
eCRF	Electronic Case Report Form	电子病例报告表
IMAS	Immunogenicity Analysis Set	免疫原性分析集
MedDRA	Medical Dictionary for Regulatory Activities	国际医学用语词典
MTD	Maximum Tolerated Dose	最大耐受剂量
MRI	Magnetic Resonance Imaging	磁共振
Nab	Neutralizing Antibodies	中和抗体
NCI	National Cancer Institute	国立癌症研究所
ORR	Objective Response Rate	客观缓解率
OS	Overall Survival	总生存期
PD	Progression	疾病进展
PD-L1	Programmed Death Ligand-1	程序性死亡受配体-1
PFS	Progression-Free Survival	无进展生存期
PK	Pharmacokinetics	药代动力学
PKAS	Pharmacokinetics Analysis Set	药代动力学分析集
PR	Partial response	部分缓解
PT	Preferred Term	首选术语
RECIST	Response Evaluation Criteria in Solid Tumors	实体瘤疗效评价标准
RP2D	Recommended Phase II Dose	II 期临床推荐剂量
SAS	Safety Analysis Set	安全性分析集
SD	Standard Deviation	标准差
SMC	Safety Monitoring Committee	安全监查委员会
SOC	System Organ Class	系统器官分类
TBIL	Total Bilirubin	总胆红素
TEAE	Treatment-Emergent Adverse Event	治疗期间不良事件
TTP	Time to Progression	至疾病进展时间
ULN	Upper Limit of Normal	正常值上限
WHO-DD	WHO Drug Dictionary	世界卫生组织药物词典

APPENDIX 1: PROTOCOL SYNOPSIS

Sponsor: CStone Pharmaceuticals (Suzhou) Co., Ltd., CStone Pharmaceuticals (Shanghai) Co., Ltd., Blueprint Medicines Corporation	
Final product name: NA	
Investigational product: CS3008 (fisogatinib, BLU-554), CS1001	
Names of active substances: Fibroblast growth factor receptor 4 inhibitor, completely humanized IgG4-type recombinant anti- Programmed death ligand 1 (PD-L1) monoclonal antibody	
Title of study:	A Muti-center, Open-label, Multiple-dose Phase Ib/II Study to Assess the Safety, Tolerability, Pharmacokinetics, Anti-tumor Efficacy of CS3008 (BLU-554) in Combination with CS1001 in Subjects with Locally Advanced or Metastatic Hepatocellular Carcinoma (HCC)
CAT No.:	JXHL1900045, CXSL900017
Protocol No.:	CS3008 (BLU-554) - 101
Sites:	20 sites as planned
Duration of the study (first subject in to last subject out):	Screening period (28 days prior to the initial administration), treatment period (at most 24 months) and follow-up period (safety follow-up period: at most 90 days; survival follow-up period: every 12 weeks until withdrawl of subjects or termination of study)
Study Phase:	Phase Ib/II

This is a multi-center, open-label, multi-dose, dose-finding and extension study for evaluating the safety, tolerance, pharmacokinetics and antitumor efficacy profiles of BLU-554 in combination with CS1001 in subjects with locally advanced or metastatic HCC.
 
The study consists of 2 parts, including a Part 1 (phase Ib) dose escalation and part 2 (phase II) dose expansion. Part 1 is a dose escalation study for determination of the MTD (Maximum tolerated dose) and/or RP2D (Recommended Phase II dose) of BLU-554 in the combination regimen and assess primary safety and tolerance of the combination regimen. Part 2 is a dose extension study in which preliminary evaluate the antitumor efficacy and the further evaluate the safety, tolerance, PK and immunogenicity of combination regimen.
	
Phase 1b: Dose Escalation	
Primary Objectives	Primary Endpoints

 To determine the maximum tolerated dose (MTD) and/or recommended Phase II dose (RP2D) of BLU-554 when being in combination with CS1001 in subjects with locally advanced or metastatic HCC. To evaluate the safety and tolerability of BLU-554 in combination with CS1001. 	
 Incidence of DLT (Dose-limiting toxicity) during the administration of BLU-554 in combination with CS1001. Safety: incidence and severity of AEs and SAEs, including laboratory tests, vital signs, and ECG Tolerance: discontinuation and reduction of study drug dose
Secondary Objectives	Secondary Endpoint

 To assess the pharmacokinetics (PK) profile of BLU-554 in combination with CS1001. 	
Pharmacokinetic parameters include, but are not limited to:
 
 When being administered in combination with BLU-554, area under the serum concentration-time curve (AUC); Maximum serum concentration (Cmax); Time to maximum serum concentration (tmax); Clearance at steady state (CLss); accumulation ratio of CS1001. When being administered in combination with CS1001, AUC, Cmax, tmax, CLss/F, accumulation ratio of BLU-554.

 To assess the preliminary anti-tumor activity of BLU-554 in combination with CS1001. 	
 To assess Objective response rate (ORR), the duration of response (DOR), disease control rate (DCR), time to progression (TTP), progression free survival (PFS) and overall survival (OS) based on RECIST v1.1.

 To assess the immunogenicity of CS1001 when being administered in combination with BLU-554. 	
 Occurrence of anti-CS1001 antibody

 To correlate FGF19 and PD-L1 expression level with efficacy of BLU-554 in combination with CS1001 	
 ORR, DOR, DCR, TTP, PFS and OS by FGF19 protein and PD-L1 protein level

Phase II: Dose expansion

Primary Objectives	Primary Endpoints

 To assess the anti-tumor activity of BLU-554 in combination with CS1001. 	
 To assess ORR based on RECIST v1.1.
Secondary Objectives	Secondary Endpoint

 To assess the anti-tumor activity of BLU-554 in combination with CS1001. 	
 To assess the DOR, DCR, TTP, PFS and OS based on RECIST v1.1

 To evaluate the safety and tolerability of BLU-554 in combination with CS1001. 	
 Safety: incidence and severity of AEs and SAEs, including laboratory tests, vital signs, and ECG Tolerance: discontinuation and reduction of study drug dose

 To assess the pharmacokinetics (PK) profile of BLU-554 in combination with CS1001. 	
Pharmacokinetic parameters include, but are not limited to:
 
 When being administered in combination with BLU-554, AUC, Cmax, tmax, CLss, accumulation ratio of CS1001. When being administered in combination with CS1001, AUC, Cmax, tmax, CLss/F, accumulation ratio of BLU-554.

 To assess the immunogenicity of CS1001 when being administered in combination with BLU-554. 	
 Occurrence of anti-CS1001 antibody

 To correlate FGF19 and PD-L1 expression level with efficacy of BLU-554 in combination with CS1001 	
 ORR, DOR, DCR, TTP, PFS and OS by FGF19 protein and PD-L1 protein level

Study design:

Both Phase Ib and Phase II can be divided into 3 periods, screening period, treatment period and follow-up period:

- The screening period is the 28 days prior to the first dose.
- During the treatment period, the subjects will be administered the study drug once every 21 days (3 cycles). BLU-554 is taken orally (PO) once daily (QD); CS1001 is administered intravenously once every 21 days (Q3W). Subjects with advanced stage solid tumor will be imageologically evaluated by the investigators every 9 weeks (i.e. every 3 dosing periods) during the 1st year of treatment and every 12 weeks after treatment for more than 1 year against Response Evaluation Criteria in Solid Tumors (RECIST v1.1). The investigator may increase evaluation frequency if clinically indicated. The drug may be administered continually until presence of intolerable adverse reaction, disease progression, withdrawal of informed consent, loss to follow up, death or study termination. The duration of treatment may be up to 24 months.
- Follow-up period consists of safety follow-up period and survival follow-up period. The safety follow-up period includes 90 days after the last dose of study drug, or until the initiation of a new anti-tumor treatment, whichever occurs earlier. Survival follow-up period will be performed every 12 weeks for collection of the survival status, subsequent anti-tumor therapies and study drug-related SAEs of the subjects until the death, loss to follow-up, withdrawal or termination of study, whichever occurs first. Refer to the Section 1.2 SOA for the study schedule.

Phase Ib: Dose Escalation

The MTD and/or RP2D of BLU-554 in the combination regimen will be determined using a BOIN dose escalation design. 2 dose levels of BLU-554 will be assessed with CS1001 1,200 mg Q3W as the fixed dose (RP2D in single-dose study). The planned dose escalation scheme is shown in Table 1 with 400 mg QD as the starting dose of BLU-554. Every 21 days (3 weeks) will be considered as one cycle. DLT assessment will be done within 21 days (Cycle 1) after the administration. Using BOIN design, the target toxicity probability of the MTD is 0.3 with a maximum sample size of 12. The cohort size included 3 enrolled and treated subjects. The number can be modified based on subject's enrollment. As shown in 错误!未找到引用源。 , the starting dose is dose level 1, i.e. BLU-554 400 mg QD in combination with fixed dose CS1001 1,200 mg Q3w. After complete DLT assessment for each cohort, the dose level for the next cohort was determined according to the dose escalation/decreasing rule in 错误!未找到引用源。 . Repeat the step with every 3 subjects until a maximum sample size of 12 is reached, the dose escalation is ended (See Dose Escalation Flowchart for details). CS1001 is administered intravenously once every 3 weeks (21 days). BLU-554 is taken orally once daily from Day 1 to Day 21; In case that the two study drugs would be administered on the same day, BLU-554 should be administered firstly.

Table 1:Planned Dose Escalation Scheme

Cohort	BUL-554	CS1001
1	400 mg QD	1,200 mg Q3W
2	600 mg QD	1,200 mg Q3W

During the study period, an SMC consisting of the principle investigator, the CRO's representatives (CRA and other relevant person) and the sponsor's representative will be established to review the safety data, PK data, efficacy data from the study and determine the escalation dose level and dosage regimen in dose escalation study so as to determine the MTD and RP2D selected for the extension study. The SMC will also decide whether or not to include unscheduled dose levels for the study.

Phase II: Dose expansion:

[figure not shown]
The primary objective of the dose expansion phase is to primarily evaluate the antitumor efficacy as well as to further evaluate the safety, tolerability, PK and immunogenicity of the combination regimen. In this part, subjects will be enrolled into 2 groups according to the expression of FGF19 immunohistochemistry (IHC): Group 1 will be advanced hepatocellular carcinoma subjects with FGF19 IHC-, the cancellation of which will be based on phase Ib data (see protocol 4.1 for details); Group 2 will be advanced hepatocellular carcinoma subjects with FGF19 IHC+. In case of being within the statistically pre-defined assessment range, additional subjects may be enrolled for further evaluation (see Protocol 4.1 for details). FGF19 expression will be determined at central laboratory by immunohistochemistry (IHC) with the inclusion criteria of FGF19 IHC+ defined as $\geq 1\%$.

In Phase Ib and Phase II, archived or fresh tumor samples must be provided for FGF19 and PD-L1 IHC test which will be employed at central laboratory.

The tumors shall be evaluated in accordance with RECIST v1.1. During the 1st year of the treatment, subjects will receive CT/MRI examination every 9 weeks (every 3 cycles). After 1 year of treatment, CT/MRI examinations shall be carried out once every 12 weeks (The investigator may increase the frequency of tumor evaluations where clinically indicated).

The data from subjects on anti-tumor activity, safety, tolerability, PK profile and host immunogenicity will be reviewed from the day of first administration of study drugs up to 90 days after the last administration or up to two-year treatment period of combination regimen

• *Dose Escalation Process:*

* DLT rate = $\frac{\text{Total number of patients who experienced DLT at the current dose}}{\text{Total number of patients treated at the current dose}}$

Planned number of subjects:	Phase Ib: Approximately 12 subjects will be enrolled Phase II: Approximately 40 subjects will be enrolled
Dose limiting toxicity (DLT) definition:	
Definition of DLT: All toxicity or adverse events (AEs) are graded according to NCI-CTCAE 5.0. Any AE occurring during C1 (21 days) that is not clearly caused by something other than investigational drug:
 
Hematological toxicity:
 
 • Grade 4 neutropenia that lasts for >7 days; • Grade ≥3 febrile neutropenia (ANC<1,000/mm³, with a single temperature of ≥38.3°C or a sustained temperature of ≥38°C for more than one hour); • Grade 3 neutropenia with infection;

	
 ● Grade 3 thrombocytopenia with clinically significantly bleeding; ● Grade 4 thrombocytopenia; ● Grade ≥ 4 anemia
	
Non-hematological toxicity:
 
 ● Grade ≥ 4 toxicity; ● Grade 3 toxicity that fails to be resolved to \leqGrade 2, with the exception of diarrhea, nausea and vomiting; ● Grade ≥ 3 immune-related adverse event (irAE); ● Any Grade 3 tumor flare reaction (local pain, irritation or rash at known or suspected tumor focus) that lasts for 7 days or above; ● Grade 3 or Grade 4 non-hematological laboratory abnormalities, if meet any of the followings: 
 – need medical intervention – require hospitalization – last for >7 days 
and other toxicity of any grade that requires premature termination of the study as determined by the investigator and the sponsor through discussion.
 
Definition of MTD: Based on BOIN design, MTD is the highest dose level at which 30% of the subjects experience DLT within 21 days (Cycle 1) among which at least 6 subjects are available for DLT evaluation. The RP2D will be determined by SMC based on comprehensive data of safety and tolerability, PK, pharmacodynamics, and preliminary anti-tumor efficacy obtained during the dose escalation phase. The RP2D will not exceed the MTD and will be determined at a dose escalation meeting.


Study Population:
	
Inclusion Criteria:
 
To meet the conditions for participation in this clinical study, subjects must:
 
 1. Voluntarily participate in the clinical study. Fully understand and get informed of this study and sign the Informed Consent Form (ICF). 2. ≥ 18 years of age on day of signing the informed consent. 3. Unresectable locally advanced or metastatic hepatocellular carcinoma as confirmed by histology or cytology. 4. Stage B or C based on Barcelona Clinic Liver Cancer (BCLC) staging system; In case of Stage B, subject must be

	
ineligible for surgery and/or local therapy, or has progressed after surgery and/or local therapy or refuses surgery and/or local treatment.
 
 5. For Phase Ib, subject has failed after or is unsuitable for the standard systemic therapy against HCC. For Phase II, subject has not previously received systemic therapy [systemic therapies mainly include: chemotherapy, molecular target drugs (e.g. tyrosine kinase inhibitors, TKI), immunotherapy (e.g. anti PD-1/PD-L1, CTLA-4 etc.), biological therapy (e.g. tumor vaccine), cytokines, etc.)]. 6. At least one measurable lesion as evaluable by RECIST version 1.1, Target lesions within the field of prior efficacy irradiation or in the area of local treatment (intervention or ablation therapy) are considered measurable in case of confirmation of progression. 7. Eastern Cooperative Oncology Group (ECOG) performance status (PS) score of 0-1 point. 8. A-level Child-Pugh score. 9. Expected survival ≥ 3 months. 10. For Phase Ib and II, 9 formalin fixed-paraffin embedded and unstained tumor tissue slides should be provided for FGF19 IHC and PD-L1 analysis in the central laboratory. 
 • Patients to be enrolled in the FGF19 IHC + arm in the Phase II study must be FGF19 IHC +; • Patients to be enrolled in the FGF19 IHC - arm in the Phase II study must be FGF19 IHC - (whether this arm will be initiated or not will be decided based on Phase Ib data) 11. Clinical laboratory screening criteria: 
 • Absolute neutrophil count (ANC) $\geq 1.5 \times 10^9/L$ • Platelet count $\geq 75 \times 10^9/L$ • Hemoglobin ≥ 90 g/L • Aspartate aminotransferase (AST) and alanine aminotransferase (ALT) $\leq 5 \times ULN$ • Total bilirubin $\leq 2 \times ULN$ • International normalized ratio (INR) or prothrombin time (PT) $\leq 1.5 \times ULN$ (INR $\leq 1.5 \times ULN$ and PT $\leq 1.5 \times ULN$, if both available) • Serum creatinine $\leq 1.5 \times ULN$ or creatinine clearance (CL) ≥ 60 mL/min (Cockcroft-Gault Formula) 
 Female: $CrCl = \frac{(140 - age) \times weight (Kg) \times 0.85}{72 \times serum\ creatinine (mg/dL)}$ Male: $CrCl = \frac{(140 - age) \times weight (Kg) \times 1.00}{72 \times serum\ creatinine (mg/dL)}$ 12. For subjects with hepatitis C virus (HCV) infection, treatment with locally approved and available anti-HCV therapy is
--	--

	
required if HCV RNA is detected.
 
13. For subjects with hepatitis B virus (HBV) infection, HBV DNA \leq 2,000 IU/ml at Screening.
 
 • Subject with HBV DNA (+), treatment with HBV antiviral therapy (as per the local standard of care) is required at least 14 days prior to the initiation of study. • Subject with HBsAg (+) and/or HBcAb (+), based on investigator assessment, HBV antiviral therapy may be applied if needed. 
14. For female subjects of childbearing potential, serum pregnancy test must be negative within 7 days prior to randomization. Except for female subjects who have been recorded as surgically sterilized or who are postmenopausal, female subjects of childbearing potential or male subjects and their partners must agree to use effective contraception from the signature of the informed consent form (ICF) until at least 6 months after the last dose of study drug. Appendix 6: Effective Contraceptive Methods
 
Exclusion Criteria: Subjects who meet any of the following criteria will not be eligible to participate in the study:
 
 1. Portal vein tumor thrombosis in the main trunk or contralateral first branch (VP4), involvement of the inferior vena cava or the heart as revealed by imaging at baseline. 2. Prior or current history of hepatic encephalopathy. 3. History of liver surgery and/or local treatment for HCC (intervention, ablation therapy, absolute alcohol injection, etc.) or radiotherapy, etc. within 4 weeks prior to first dose. 4. Active or documented gastrointestinal bleeding within 6 months (e.g. esophageal or gastric varices, ulcer bleeding). 5. Presence of ascites detected by physical examination or clinical symptoms caused by ascites during the screening period, or ascites that need for special treatment, such as repeated drainage, or intraperitoneal drug infusion, etc. (Note: subjects with a small amount of ascites that can only be detected by imaging may be enrolled). Presence of uncontrolled pleural effusion or pericardial effusion (with clinical symptoms, requiring repeated drainage, or intrapleural or pericardial drug infusion, etc.) during the screening period. 6. Presence of meningeal metastasis or central nervous system (CNS) metastatic lesions. 7. According to the New York Heart Association (NYHA) Classification, subject has clinically significant, uncontrolled cardiovascular disease, including Grade III or IV congestive heart failure; myocardial infarction or unstable angina (within 6 months), uncontrolled hypertension (systolic blood pressure \geq 150 mmHg and diastolic blood pressure \geq 100
--	---

	
mmHg) or clinically significant uncontrolled arrhythmias, including bradycardia that may result in prolonged QT (e.g. Grade II or III heart block). Left ventricular ejection fraction (LVEF)<50%. QTc interval >480 msec (corrected using Fridericia's formula).
 
 8. Subjects who have current interstitial lung disease or noninfectious pneumonitis, and prior history of interstitial lung disease or noninfectious pneumonitis that may affect the assessment or management of study drug-related pulmonary toxicity. Presence of active tuberculosis infection. 9. Any serious acute, chronic infections that require systemic antimicrobial, antifungal or antiviral therapy at screening, excluding viral hepatitis. 10. Malabsorption syndrome or inability to take the study drug orally for other reasons. 11. Had primary malignancies other than HCC within 5 years. The following prior malignancies were excluded: completely excised skin basal cells and squamous cell carcinoma, local prostate cancer responsive to treatment, and carcinoma in situ with complete resection at any site. 12. Subject has had major surgery within 4 weeks prior to first dose (procedures such as central venous cannulation, biopsy, and feeding tube placement are not considered as major surgery). 13. Previously received FGFR4 inhibitor treatment. 14. Blood transfusion, use of hematopoietic stimulating factors [including G-CSF (granulocyte colony stimulating factor), GM-CSF (granulocyte-macrophage colony stimulating factor), EPO (erythropoietin) and TPO (thrombopoietin)] and human albumin preparations within 14 days prior to first dose. 15. Requiring corticosteroids (dose equivalent to > 10 mg/day of Prednisone) or other immunosuppressive drugs within 14 days prior to first dose for systemic therapy. Note: For the absence of active autoimmune disease, it is allowed to use inhaled or topical steroids or adrenal hormone replacement therapy with equivalent dose of ≤10 mg/day prednisone. Short-term (≤ 7 days) use of corticosteroids for prophylaxis (e.g., contrast allergy) or for the treatment of non- autoimmune diseases (e.g., delayed hypersensitivity reactions due to contact allergens) is permitted. For subjects requiring hormone therapy, the dose administration should be done at least two days before and after the injection of CS1001. 16. Use of traditional Chinese medicine (elemene, Kanglaite, Cinobufacin, Xiaoaiping, Huaier granule, Ganfule, Jinlong capsule, Aidi, etc.) with anti-liver cancer indication within 14 days prior to the first dose. 17. Subject has received potent CYP3A4 inhibitors and/or inducers within 2 weeks prior to first dose. See Appendix 8: Strong Inhibitors and Inducers of CYP3A4. 18. Concurrent HBV and HCV infection (History of HCV infection, but subjects with HCV RNA(-) can be considered
--	--

	
as not being infected with HCV).
 
19. Subjects with human immunodeficiency virus (HIV) infection.
 
20. Pregnant or lactating women.
 
21. Subjects with a history of hypersensitivity or hypersensitivity to any of the components of the investigational drug.
 
22. Any previous or current clinically significant diseases, medical conditions, history of surgery, signs, or abnormal laboratory parameters that, in the opinion of the investigator, may increase the risks associated with study participation and study drug administration, or affect the subject's ability to receive study drug and reliability of study results; other circumstances that in the opinion of the investigator would preclude participation in the study.
 
23. Subjects who are unwilling or unable to follow the study procedures as defined. Subjects with no or limited disposing capacity and with psychiatric disorders that may affect study compliance.
 
24. With the exception of alopecia, all toxicities from prior anticancer therapies and other therapies did not recover to \leq Grade 1 (per CTCAE v5.0) prior to the first dose of study drug.
 
25. Subjects who have received prior allogeneic stem cell or solid organ transplantation.

Definition of end of study:	All subjects completed the treatment period, EOT visit, disease progression follow-up and survival follow-up or the Sponsor terminated the study (whichever occurred first).
Test product, dose and mode of administration:	
BLU-554 capsule 100 mg will be taken by oral administration once daily.
 
CS1001 injection 600 mg/20 ml/Bottle will be given via intravenous infusion on the first day of each treatment cycle, once every 21 days (3 weeks).

Planned trial and treatment duration per subject:	No more than 35 cycles (24 months) of study treatment followed by a 90-day safety follow-up.

Statistical methods:

Analysis Populations

Safety analysis set: consists of all subjects receiving at least one dose of investigational product.

Efficacy analysis set: consists of all subjects with measurable baseline disease who received at least one dose of investigational product. It will be the primary analysis set for efficacy in this study. Note: Subjects who were screened but never started treatment will be listed, but not included in any efficacy analysis set. Therefore, these subjects will not be included in any of the summary tables.

